CURRICULUM REFINEMENT: This involves the review, presentation, refinement and final presentation of teaching materials used in international HIV teaching settings to teach clinic staff members palliative skills for populations known to be difficult to engage and retain in outpatient HIV care. Evaluation forms for feedback are identified by a unique code for each participant. The Research Team is aware that there will be only 1 representative of each discipline and, for the most-part, responses will not have identifying mechanisms. No responses will be linked externally in an identifiable manner in dissemination efforts. Feedback from each discipline will be useful in refinement of the curriculum.

2 * Describe all procedures already being performed for diagnostic or treatment purposes (if not applicable to the study, enter "N/A"):

N/A This is an educational intervention and there are no procedures being performed.

Point of Information:

PATIENTS - Standard OUTPATIENT HIV CARE:

HIV patients are routinely monitored as outpatients every 3-6 months with laboratory testing specifically CD4 cell count and HIV PCR (viral Load) measurements as well as electrolytes and liver panels with yearly screening for co-occurring illness. At each visit a history and physical is documented along with current medications and management strategies. We will review this information from the electronic medical record (EMR) to be correlated with patient survey responses.

3 * Describe the duration of an individual participant's participation in the study:

Following the informed consent process:

1) INTERVENTION RECIPIENT - STAFF:

- a) Members of the HIV clinic STAFF Team (CASA Team) will participate in the training that has 3 parts and takes place over about 18 - 24 months. At this time the initial training time has not been determined with the clinic administration. It will be submitted to the IRB before staff participate in the study.
- b) Selected clinic staff will participate in Baseline and 1 follow-up survey. Questions on this survey are related to work-related stress and response to the educational intervention.
- c) Clinic staff participating in 1-time qualitative interviews will be consented prior to the interview

LONGITUDINAL DATA COLLECTION:

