Several unadjusted and adjusted Cox Proportional Hazard regression models will be estimated for comparing survival curves between Site 1 and Site 2 including models that allow for time-varying correlates [e.g., Cox-Aalen (97)]. Evidence of a short-term intervention effect on attendance (retention in care) will be made by comparing survival curves at both sites from 8 months (prior to the baseline assessment) to 16 months following the initiation of the intervention training at Site 1. Descriptive analyses and identification of sample heterogeneities and potential sources of bias. Summary statistics and graphical displays will present characteristics of study participants in each intervention arm as reported at B, F1, and F2, as well as to describe aggregate change of time-varying measures over three time periods: B to F1 (short-term gains), B to F2 (longer-term), F1 to F3 (maintenance).

BIAS: Analyses will be conducted to identify potential sources of bias that may require statistical redress in multivariate analyses. Characteristics of participants in the experimental arm at B will be compared to those of patients in the Control group to identify potential heterogeneities between samples. Given the nonrandom assignment of patients to study arm, it will be necessary to compare characteristics of participants in the study arms at B to identify potential heterogeneities between sites with regard to the distributions of patient or other background characteristics that research suggests might be related to patient outcome(s). Characteristics of participants at B will be compared on the basis of their level of study completion (only B, B+F1, or B+F1+F2) to assess attrition and identify its potential correlates. Between-group comparisons within a single interview will be made with chi-square, t-tests (Fisher's exact as appropriate) or one-way ANOVA with F-tests of significance; and comparisons of change across time assessed by paired Student's t-test or paired Wilcoxon test. Concordance between measures at different times will be assessed using correlation coefficients: Pearson or Kendall tau/Spearman. Probit modeling will be used to determine whether specific patient characteristics, stressors, and/or modifiers are associated with attrition.(119) Propensity analyses (93) will be conducted to calculate terms to control for potential unbalance between intervention arms (see "Propensity Scores" below) will be used.

Addressing Aim 3. CURRICULUM:

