o HIV Disease Control Status (unable to initiate therapy; on therapy-HIV controlled; on therapy-HIV not controlled; documented treatment failure; other), viral load suppression (Y/N) [SO]; a dummy variable noting whether the patient was defined as lost-to-follow-up (no contact w/patient > 2 months); and a variable noting persistence of attendance (# of appointments attended in each quarter of the prior year) [SO].

Family History of Substance Abuse 3 questions

o Monthly clinic data for patients will be coded from 6 months prior to accrual into the study until 18 months follow-up.

STAFF Questionnaires are given to the staff who receive the teaching intervention in 2015. There are 2 instruments to measure staff stress related to caring for persons with HIV disease.

2 *Upload a copy of all questionnaires/surveys:

Name	Created	Modified Date
ADDITIONAL questions STAFF.docx	7/21/2016 12:13 PM	7/21/2016 12:13 PM
Staff Questionnaire_v8.26.15. clean copy.doc	8/26/2015 10:18 AM	8/26/2015 10:35 AM
Patient Follow-upSurvey1_v7.7.15	7/7/2015 4:44 PM	7/7/2015 4:44 PM
Patient Total Survey v7.7.15	7/7/2015 4:43 PM	7/7/2015 4:43 PM
Patient Total Survey v5.5.15	5/11/2015 1:27 PM	5/19/2015 11:31 AM
Staff Questionnaire_v11.2014-2.doc	12/1/2014 1:26 PM	12/1/2014 1:26 PM
FINAL_Family History of Substance Abuse (2).docx	10/14/2014 6:57 PM	10/14/2014 6:57 PM
Patient's Total Survey_v6.27.14	7/2/2014 1:02 PM	7/2/2014 1:02 PM
POS_Touch Pad	7/2/2014 1:01 PM	7/2/2014 1:01 PM
Burnout inventory	5/16/2014 1:11 PM	5/16/2014 1:11 PM
AIDS Stress Scale	5/16/2014 1:11 PM	5/16/2014 1:11 PM
FAMCARE Scale.pdf	12/19/2013 4:40 PM	12/19/2013 4:40 PM
Sexual-Behaviors.pdf	12/19/2013 4:39 PM	12/19/2013 4:39 PM
Health Care Power of Attorney.pdf	12/19/2013 4:34 PM	12/19/2013 4:34 PM
POS.pdf	12/19/2013 4:34 PM	12/19/2013 4:34 PM
McGill-QOL.pdf	12/19/2013 4:34 PM	12/19/2013 4:34 PM
Rosenberg Self-Esteem Scale.pdf	12/19/2013 4:34 PM	12/19/2013 4:34 PM
Alcohol-Drug-Use_Mental-Illness.pdf	12/19/2013 4:34 PM	12/19/2013 4:34 PM
Life-Events-Checklist.pdf	12/19/2013 4:33 PM	12/19/2013 4:33 PM
AACTG_Adherence.pdf	12/19/2013 4:33 PM	12/19/2013 4:33 PM
HIV Symptom Index.pdf	12/19/2013 4:33 PM	12/19/2013 4:33 PM
ECOG Performance Status.pdf	12/19/2013 4:32 PM	12/19/2013 4:32 PM
Demographics.pdf	12/19/2013 4:32 PM	12/19/2013 4:32 PM

3 *What is the total length of time that each survey is expected to take?

The STAFF Questionnaires take less than 5 minutes to complete.

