Name: v2_Vulnerable Populations

View: v2_Vulnerable Populations - Employees or Lab Personnel

Vulnerable Populations - Employees or Lab Personnel

You indicated that employees or lab personnel are included in this study.

1 * **Describe how you will ensure participation in this research will not affect employment and prevent undue influence:**
We will explain to all participants that participation is voluntary and that they do not have to take part in this study. If they choose not to participate or withdraw participation, there will be no adverse consequences. It will not affect their employment or care.

Enrollment in this study is voluntary and each participant will sign a consent form that documents his/her right to withdraw at any time and stating that participation in this study or not will not impact their rights, care or employment status.

View: v2_Vulnerable Populations - Students

ID: VIEW4E0E5192BA800
Name: v2_Vulnerable Populations - Employees or Lab Personnel

Vulnerable Populations - Students

You indicated that students are included in this study.

1 * **Describe the types of students that are included in this study:**
We will not actively target students for this study, but will allow them to participate if they meet the eligibility criteria.

2 * **Describe how you will prevent undue influence.**
As previously stated for employees, we will inform them that participation is voluntary and that they do not have to participate. If they choose not to participate or decide to withdraw from the study, there will not be any adverse affects.

View: v2_Eligibility

ID: VIEW4E0E519F32000
Name: v2_Vulnerable Populations - Students

Eligibility

1 * Do you have an existing Eligibility checklist(s) for this study?
 Yes No

1.1 If Yes, upload here. If you need a template, you can download it by clicking [HERE](#). The checklists you upload will also be available under the Documents tab of this application.

Name	Created	Modified Date
There are no items to display		

1.2 If No, create an eligibility checklist below:

List inclusion criteria (List each Inclusion Criteria individually, using the ADD button):

Number Criteria

View	PATIENT Inclusion Criteria (See Attachments for STAFF Eligibility)
View 1	1) HIV positive
View 2	2) Male
View 3	3) Male who has sex with men
View 4	4) Age 18 - 35 years
View 5	5) Attend either of the 2 University of Maryland clinics (Jacques Initiative or Evelyn Jordan Center)

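### The retention survival window does not match the months to be coded, and it puts pre-enrolment and pre-training time into a site comparison meant to show a training effect

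*Combined protocol and SAP*

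**What the plan says.** **Analysis window.** In Sample Size and Data Analysis, question 2, under Survival Analysis, the plan estimates Cox models comparing the two sites. The purpose is given as "Evidence of a short-term intervention effect on attendance (retention in care", and the method is "comparing survival curves at both sites from 8 months (prior to the baseline assessment) to 16 months following the initiation of the intervention training". The start of this window is tied to baseline and the end to the training date at Site 1. The models may include "models that allow for time-varying correlates", but training status is not named as one. The section gives no event, no rule for entry into the risk set and no censoring rule.

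**Data window.** Surveys/Questionnaires, question 1, under the medical record abstraction, says: "Monthly clinic data for patients will be coded from 6 months prior to accrual into the study until 18 months follow-up". Both ends are tied to accrual. The same list contains an indicator for "lost-to-follow-up (no contact w/patient > 2 months" and a count described as "persistence of attendance (# of appointments attended in each quarter of the prior year". Neither is linked to the Cox model.

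**Entry.** The patient inclusion criteria under Eligibility require that patients "Attend either of the 2 University of Maryland clinics".

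**Timing.** Research Design puts patient enrolment from Month 7 to about Month 24 and equates Month 13 with November 2014. Study Procedures, question 4, places the intervention in January 2015.

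**The concern.** Two things do not fit. First, the curves start earlier than the monthly coding does, and for early enrolees they end later.

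Second, a comparison of sites over this window is not a comparison of trained with untrained care. Part of each patient's time comes before he joined the study. For patients enrolled before January 2015, part of the time after joining comes before anyone was trained. The clinics were not randomised, so a difference between them before training is quite possible. A single site hazard ratio over the whole window would mix that difference with any effect of training.

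Retention in care is a named patient aim, and this is the analysis offered as evidence of a short-term effect on it.

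**Working it through.** **Inputs.** Enrolment month m = 7 to 24 (Research Design, Phase 1). Month 13 is November 2014 (Phase 2), so January 2015 is Month 15. The window ends at 15 + 16 = Month 31 (May 2016). I take accrual to be baseline. Averages assume even accrual over the 18 months; the documents do not give the accrual pattern.

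**The plan's own figures.** Both spans add to 24 months: 8 + 16 and 6 + 18. The window has that length only for a patient enrolled in the month training starts, and even then the two spans are offset by 2 months. The Sample Size section also gives n = 140 for the Cox comparison. It cannot be reproduced, because no hazard ratio or event probability is stated. Assuming two-sided 0.05, power 0.80 and equal groups, the detectable hazard ratio is exp(−2 × (1.960 + 0.842)/√events). That is 0.62 with 140 events, 0.51 with 70 and 0.35 with 28. So n = 140 does not reveal which event was meant.

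**Window against coded months.** The window is [m − 8, 31]. The coded months are [m − 6, m + 18].

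- Front: (m − 6) − (m − 8) = 2 months without monthly coding, for every m.
- Back: max(0, 31 − (m + 18)) = max(0, 13 − m). This is 6 months for m = 7, 1 for m = 12 and 0 from m = 13.

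**What the window contains.** Its length is 31 − (m − 8) = 39 − m, mean 39 − 15.5 = 23.5 months. Time between enrolment and training is max(0, 15 − m).

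| Enrolled | Window | Before enrolment | Enrolled, before training |
|---|---|---|---|
| Month 7 | 32 | 8 (25%) | 8 |
| Month 15 | 24 | 8 (33%) | 0 |
| Month 24 | 15 | 8 (53%) | 0 |
| Mean | 23.5 | 8.0 (34%) | 36/18 = 2.0 |

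On average 8.0 + 2.0 = 10.0 of 23.5 months (43%) fall before enrolment or before training.

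**Consequence by type of event.**

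- *Permanent loss.* A patient must attend a study clinic to enrol, so he cannot have been lost for good beforehand. All patients at both sites carry the same 8 event-free months. No event occurs in them, so the Cox comparison is unchanged and the lead-in adds nothing.
- *A gap in care.* Gaps can arise before enrolment or before training. They then enter the site comparison as if they bore on training, unless training status varies with time in the model.

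**The case against.** The strongest reply is that much of this is untidiness rather than error. Several parts of it stand.

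- A reader might infer that the window cannot be filled at all. That goes too far. If the quarterly count is taken at baseline, it reaches back a year and covers the 2 front months in coarse form. The back-end shortfall is administrative right-censoring, which Cox regression handles.
- A reader might infer that a site enrolling later would look better retained. That needs three things the documents do not state: a window starting 8 months before training rather than before baseline, permanent loss as the event, and different accrual timing at the two sites.
- A reader might infer that the loss indicator of more than 2 months is the Cox event and is wrong because "HIV patients are routinely monitored as outpatients every 3-6 months". The plan does not assign it to the model. It is also defined by contact, not visits, and Sample Attrition says the clinics have outreach workers.
- The unnamed event is, by itself, missing detail. Listed attachments that are not reproduced, such as the data collection list and the research plan, may supply it.
- A pre-training period suits a pre-post design, and the plan does permit time-varying terms.

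The last point does not settle the matter. Permitting time-varying terms is not the same as specifying that the training effect is the change at Site 1 relative to Site 2. As written, the evidence is a comparison of two curves over time that mixes before and after.

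**Conclusion.** The point holds in a limited form and should be corrected. The two windows disagree by 2 months at the front for every patient. The difference at the back, up to 6 months for patients enrolled before Month 13, costs information but is not bias.

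The substantive fault is that pre-enrolment and pre-training time enters a site comparison offered as evidence of a training effect. Under even accrual, with training in January 2015, this is about 43% of window time. Whether it distorts the result depends on the event: the pre-enrolment part is harmless for permanent loss but not for a gap in care. No size of bias in the hazard ratio can be given from the documents.

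Study Procedures also gives April 2014 as the start of data collection. That would make the largest back-end shortfall 7 months and leaves the 2-month front gap as it is.

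It would be wrong to read this as undermining the study. The main sample size rests on viral suppression, and attendance is also analysed descriptively.

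**What to change.** 1. Make the windows in Survival Analysis and in the abstraction list agree, using the months already planned for coding. State a data cut-off: coding to 18 months for a Month-24 enrolee runs to Month 42, one month past the extended study end of March 2017 (Month 41).
2. Start time at risk at enrolment. Use coded pre-enrolment attendance only as a baseline covariate.
3. Fit site, a time-varying term for before or after January 2015, and their interaction. Take the interaction as the training effect.
4. State one event, the same at both sites. If it is a gap in attendance, date it at the start of the gap (the last attended visit) and end follow-up one gap length before the last coded month. Then no patient is at risk while the event is impossible.

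A tempting alternative is to date a gap of over 6 months at its end and let patients enter at the later of enrolment and training start. This recreates event-free time. If baseline is an attended visit, no such gap can be completed in the first 6 months after it. Enrolees in Months 15–24 lose 6 months each (60 in total) and those in Months 10–14 lose 1 to 5 (15 in total), a mean of 75/18 = 4.2 months. It differs by enrolment month, and a fixed enrolment-month covariate does not remove it.

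**Cost.** This is a change of wording and needs no new coding. Usable follow-up is shorter and there are fewer events. With a 6-month gap as an illustration, time at risk falls from 18 to 12 months per patient. Pre-training information is limited, because only Months 7–14 contribute: 8/18 × 204, about 91 patients. They give 204 × 2.0 = 408 patient-months out of 204 × 12 = 2,448 (17%). The interaction will therefore be imprecise. With one clinic per arm, it also assumes that the two clinics would otherwise have changed alike.
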